4.5. Baseline and Analysis Window/Visit

Unless otherwise specified, (pre-prime) baseline is defined as the last non-missing value before the prime vaccination on Day 1. Pre-boost baseline is defined as the value collected prior to the boost vaccination (Day 85/Visit 5), with the earliest value being used as Visit 4 (Day 78) and the latest value being the day of boost vaccination (but prior to vaccination being given).

The pre-prime baseline will be used for prime data analysis/summaries and the pre-boost baseline will be used for boost data analysis/summaries, both are based on the Immunogenicity Analysis Set.

No analysis window mapping will be applied. Visit based endpoints will be reported based on study visits as collected for scheduled visits. Any unscheduled visit will be reported as unscheduled visit relative to each study vaccination. (e.g. unscheduled visit after prime dose and unscheduled visit after boost dose)

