7.7.1 Analysis of Primary Immunogenicity Endpoint

Summaries and analysis of immunogenicity data will be presented for the Immunogenicity and Per Protocol Analysis Set. For immunogenicity data in the prime period, subjects in the Prime Immunogenicity Analysis Set will be grouped into BPZE1 prime (A+B) and Boostrix prime (C+D) arms. For immunogenicity data in the boost period, subjects in the Boost Immunogenicity Analysis Set will be grouped to BPZE1 prime with BPZE1 boost (A), BPZE1 prime with no boost (B), Boostrix prime with BPZE1 boost (C) and Boostrix prime with no boost (D). In addition, as multiple antigens are being tested across vaccine combinations, all possible treatment group combinations will be displayed. For priming data analysis, the primary endpoint will be based on nasal mucosal immunogenicity change from screening, and for boost data analysis that will be based on screening and Day 78 prior to boost vaccination. The Immunogenicity and Per Protocol Analysis Sets will be used for sensitivity analysis.

The proportion and 95% CI of subjects who achieve seroconversion at Day 29 for prime vaccination and Day 113 for boost vaccination will be analyzed. Seroconversion is defined as a 2-fold increase over the baseline value or a 4-fold increase over the minimal limit of assay detection in S-IgA ELISA from nasal secretions for any of the pertussis-specific antibodies (S-IgA ELISA): PT, FHA, PRN, FIM 2/3, or BPZE1 whole cell extract). Baseline is defined as the value at screening.

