7.7.3 Analysis of Secondary Immunogenicity Endpoint

The secondary nasal **mucosal** immunogenicity endpoints will be summarized by treatment arm. Analyses will include the GMTs along with corresponding 95% CIs and GMFRs from baseline at each time point and maximum titer or ratio at any time point, as well as the proportion of subjects with seroconversion, defined as a 2-fold increase in S-IgA over baseline or 4-fold over the minimal limit of assay detection at any time point and at each time point. The baseline refers to screening and Day 78 prior to boost vaccination.

Systemic immune responses in terms of seroconversion of IgG and IgA antibody titers (PT, FHA, PRN, FIM 2/3, or BPZE1 whole cell extract for IgG only) will be summarized by treatment arm. Analyses will include the GMTs along with corresponding 95% CIs and GMFR at each time point and maximum titer or ratio at any time point, as well as the proportion and 95% CI of subjects achieving seroconversion (defined as 2-fold increase over baseline or 4-fold increase over the minimum limit of detection) at any time point and at each time point.

Colonization data will be summarized by treatment arm at available time points. Analysis will include dichotomized results (Yes/No) for *B. pertussis* culture along with colony counts from Days 92 to 113 following vaccination with BPZE1 or placebo. The effect of recent and post vaccination with BPZE1 on absolute colony counts and clearance of colonization will be assessed for this period. The analyses will include proportion of subjects with positive *B. pertussis* at Day 78 (prior to boosting vaccination) as well as Day 254 (end-of-study).

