3.2. Study Endpoints

3.2.1. Primary Endpoints

3.2.1.1 Primary Immunogenicity Endpoints

- **Mucosal seroconversion (nasal mucosal secretion sampling):** Proportion of subjects who achieve seroconversion against at least 1 pertussis antigen (PT, FHA, PRN, FIM 2/3, or BPZE1 whole cell extract) in nasal secretions on Day 29 or 113 (prime or prime + boost).

Mucosal seroconversion is defined as a 2-fold increase over the baseline value (collected during screening) or a 4-fold increase over the minimal limit of assay detection (whenever the baseline value falls below the limits of assay detection) for any of the pertussis-specific antibodies (S-IgA ELISA): PT, FHA, PRN, FIM 2/3, or BPZE1 whole cell extract. Seroconversion will be calculated based on absolute titer response over baseline **and** by standardizing pertussis specific ELISA responses relative to non-pertussis specific total mucosal secretion (Total IgA).

Mucosal baseline samples will be taken at the screening visit.

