8.1. Primary Immunogenicity Analyses

The primary immunogenicity endpoint of this study is mucosal seroconversion (nasal mucosal secretion sampling) defined as the proportion of subjects who achieve seroconversion against at least 1 pertussis antigen (PT, FHA, PRN, FIM 2/3, or BPZE1 whole cell extract) in nasal secretions on Day 29 for the prime vaccination or Day 113 for the prime + boost vaccination.

Mucosal seroconversion is defined as a 2-fold increase over the baseline value (collected during screening) or a 4-fold increase over the minimal limit of assay detection (whenever the baseline value falls below the limits of assay detection) for any of the pertussis-specific antibodies (S-IgA ELISA): PT, FHA, PRN, FIM 2/3, or BPZE1 whole cell extract.

Seroconversion will be calculated based on absolute titer response (based on IgA) over baseline **and** by standardizing pertussis specific ELISA responses relative to non-pertussis specific total mucosal secretion (Total IgA). Overall mucosal seroconversion defined as either seroconversion based on absolute titer response (based on IgA) or seroconversion based on standardizing pertussis specific ELISA responses relative to non-pertussis specific total mucosal secretion (Total IgA).

Any pertussis antigen specific antibody titer (PT, FHA, PRN, FIM 2/3, or BPZE1 whole cell extract) from nasal mucosal sample that is below the minimal limit of assay detection will be imputed with a value equal to half of the minimal limit of assay detection of the antigen specific antibody titer.

The proportion of subjects who achieved mucosal seroconversion on Day 29/Visit 3 or Day 113/Visit 8 will be summarized based on the Immunogenicity Analysis Set. Baseline is defined as the last non-missing value collected before the prime vaccination.

Data will be summarized using frequency counts and percentages.

A by-subject listing will be provided for mucosal immunogenicity data as collected based on Immunogenicity Analysis Set.

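### SAP 4.5 assigns the pre-boost baseline to all boost data with no exception for Day 113 seroconversion, which conflicts with SAP 8.1; Protocol 7.7.1 carries both references

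*SAP*

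**What the plan says.** The primary immunogenicity endpoint is mucosal seroconversion to one or more of five antigens. SAP 8.1 assesses it in "nasal secretions on Day 29 for the prime vaccination or Day 113 for the prime + boost vaccination".

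**Pre-prime reference.** The endpoint definition in SAP 3.2.1.1 reads "Mucosal seroconversion is defined as a 2-fold increase over the baseline value (collected during screening" and then closes the bracket; Protocol 2.4.1 and 7.1 agree. SAP 8.1, having named Day 113, adds: "Baseline is defined as the last non-missing value collected before the prime vaccination". The schedule has no nasal antibody sample on Day 1, so this value and the screening value are the same sample. SAP 8.2.1.1 to 8.2.1.4 set the serum seroconversion endpoints against the pre-prime baseline, and SAP 8.2.2 carries those summaries over to the mucosal endpoints.

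**Pre-boost reference.** SAP 4.5 sets the general rule: "The pre-prime baseline will be used for prime data analysis/summaries and the pre-boost baseline will be used for boost data analysis/summaries".

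**Both.** For the primary endpoint, the first paragraph of Protocol 7.7.1 says "for boost data analysis that will be based on screening and Day 78 prior to boost vaccination"; its second paragraph gives screening as the baseline. For the secondary mucosal endpoints, Protocol 7.7.3 says "The baseline refers to screening and Day 78 prior to boost vaccination", without separating seroconversion from fold rise.

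A 2-fold rise over Day 78 already has its own secondary endpoint, called boosting (Protocol 2.5.2, SAP 3.2.2.2). SAP section 11 declares no change from the protocol's planned analyses.

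**The concern.** Day 113 is one of the two time points of the primary endpoint, and its reference sample is not the same everywhere in the plan. The two references answer different questions. Against screening, Day 113 measures what the two-dose series achieved, which is the primary objective. Against Day 78, it measures only what the second dose added.

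Under the second reading, a subject whose prime response lasts and who rises a little further can fail, so a durable prime counts against the vaccine. The result would also come close to the boosting endpoint. The analysed subjects might change as well, because a Day 78 reference needs a valid pre-boost sample. The secondary seroconversion summaries at Days 113, 169 and 254 are exposed to the same general rule.

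**Working it through.** **1. Does the SAP 4.5 rule reach Day 113?** SAP section 4 describes the boost period as the time at or after boosting, and SAP 8.1 labels Day 113 as prime + boost. Day 113 is therefore boost data. The only qualifier in SAP 4.5 is in another sentence: "Unless otherwise specified, (pre-prime) baseline is defined as the last non-missing value before the prime vaccination on Day 1". It modifies the definition of the pre-prime baseline, not the rule for boost data. Read literally, the rule covers Day 113 seroconversion.

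**2. The plan's own precision table.** Clopper-Pearson limits are the 2.5% quantile of Beta(x, n−x+1) and the 97.5% quantile of Beta(x+1, n−x).
- n = 100, x = 50: 39.83 to 60.17, width 20.34 (plan: 20.3).
- n = 100, x = 90: 82.38 to 95.10, width 12.72 (plan: 12.7).

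All 20 cells of SAP Table 4-1 (Protocol Table 7-1) reproduce within 0.05 points. The assumed response rates of 50% to 90% are not tied to either baseline.

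**3. One subject under both references.** Let F1 = Day 113 / screening and F2 = Day 113 / Day 78. Then F2 = F1 / (Day 78 / screening). As an assumed example, take a 2.83-fold rise (2^1.5) at Day 78 and a 4-fold rise at Day 113. F1 = 4 is a success. F2 = 4 / 2.83 = 1.41 is a failure. To succeed over Day 78, this subject would need 2 × 2.83 = 5.66-fold over screening.

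**4. Size at group level.** The documents give no nasal S-IgA fold rises or standard deviations, and SAP 8.2.1 leaves the detection limits to assay validation, so every input here is assumed. With normal log2 fold rises, rate = Φ((log2 F − 1) / SD), where F is the geometric mean fold rise and SD the log2 standard deviation, taken as equal for both references.

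| F1 | F2 | SD | Rate over screening | Rate over Day 78 | Gap (points) |
|---|---|---|---|---|---|
| 2 | 2 | 1.0 | 50.0% | 50.0% | 0 |
| 6 | 3 | 1.0 | 94.4% | 72.1% | 22.3 |
| 2 | 1 | 1.0 | 50.0% | 15.9% | 34.1 |
| 4 | 1.41 | 1.2 | 79.8% | 33.8% | 45.9 |
| 4 | 1.41 | 0.8 | 89.4% | 26.6% | 62.8 |
| 8 | 1 | 0.75 | 99.6% | 9.1% | 90.5 |

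For example, row 3: Φ((1 − 1)/1) = 50.0% and Φ((0 − 1)/1) = 15.9%. Over the grid F1 2 to 8, F2 1 to 4 with F2 ≤ F1, and SD 0.75 to 2.0, the gap runs from 0 to 90.5 points. It is zero when nothing of the prime response remains at Day 78 (F1 = F2). It is largest when a strong prime response persists and the second dose adds nothing.

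**5. Closer to the actual endpoint.** A simulation of success on any of five equally correlated antigens (F1 2 to 8, F2 1 to 3, SD 0.75 to 1.5, correlation 0.3 to 0.9) gives 0 to 83.9 points. With F1 = 8, F2 = 3, SD 1.5 and correlation 0.3, the rates are 99.9% and 96.3%, a gap of 3.6 points. With F1 = 8, F2 = 1, SD 0.75 and correlation 0.9, they are 99.9% and 16.0%, a gap of 83.9 points.

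**The case against.** The strongest reply is that the plan already answers the question where it matters. Every definition of the primary endpoint names the screening sample, and SAP 8.1 fixes the pre-prime value with Day 113 in view. SAP 8.2.1 confines the pre-boost value to the boosting responder and the fold rise over pre-boost, and says that baseline otherwise means pre-prime. A specific rule normally overrides a general one, so a programmer working from SAP section 8 would use the right sample. Protocol 7.7.1 and 7.7.3 can also be read as additive, with both references reported. The study tests no hypothesis, and the boosting endpoint shows the Day 78 comparison in any case.

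Much of this stands. A reader might infer that the primary endpoint has two rival definitions of equal standing; the documents do not support that. A reader might also take a particular gap, such as the 46 to 63 points in the 4-fold example, as the expected shift in the primary rate. No document figure supports any such value, and the example models one antigen, whereas the endpoint allows any of five and either the absolute or the standardised titre.

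The reply does not remove the conflict. Protocol 7.7.1 is itself specific to the primary endpoint and names Day 78. Because SAP section 11 declares no change from the protocol, a reader cannot tell whether Day 78 is still intended or was dropped without being declared.

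**Conclusion.** The conflict is real and touches the primary endpoint. It is an unrestricted general rule in SAP 4.5, together with loose wording in Protocol 7.7.1 and 7.7.3, set against a consistent body of endpoint-specific text that uses the pre-prime value. Only seroconversion at Day 113 and later is affected.

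The effect cannot be sized from the documents. It could be nil, or it could exceed the planned interval width several times over, depending on how much of the prime response remains at Day 78. The ranges shown assume lognormal fold rises, equal spread for both references, a Day 78 level on average not below screening, and no missing samples. They apply only the 2-fold rule and do not model the 4-fold rule over the detection limit. The case for a fix rests on the contradiction in the text, not on any one figure.

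**What to change.** - **SAP 4.5:** add that seroconversion at every visit, including Days 113, 169 and 254, is relative to the pre-prime baseline (mucosal: screening; serum: Day 1), and that the pre-boost baseline is used only for the boosting-responder and GMFR-over-pre-boost endpoints.
- **Protocol 7.7.1:** make screening the baseline for primary Day 113 seroconversion. If a Day 78 reference was also intended, keep it and label it supportive.
- **Protocol 7.7.3:** keep Day 78, but restrict it to the boosting and GMFR-over-pre-boost endpoints. Striking it altogether would go too far, because the sentence also serves the planned fold rise over Day 78.

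The cost is a few sentences in each document. All the samples are already scheduled, and both comparisons remain reported. The change should be in place before the Day 113 database lock.

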4.6. Handling of Missing Data

Data will be presented in the listings as reported. For summaries and analysis, the following conventions apply.

Immunogenicity Data

No Imputation methods will be used for missing immunogenicity data and all analyses will be based on complete records only.

Any pertussis antigen specific antibody titer (PT, FHA, PRN, FIM 2/3, or BPZE1 whole cell extract) from either serum or nasal mucosal sample that is below the minimal limit of assay detection will be imputed with a value equal to half of the minimal limit of assay detection of the antigen specific antibody titer.

Adverse Event Data

Missing date will be imputed as described in [Appendix 13.4](#). Missing information regarding ‘relationship to study vaccine’ or ‘severity’ will be imputed as related to study vaccine and severe, as the worst-case scenario.

Prior/Concomitant Medication Data

Missing date will be imputed as described in [Appendix 13.4](#).

5. Subject Disposition

5.1. Disposition

The number of subjects who were randomized and not randomized, the eligibility criteria met/failed will be summarized based on all screened subjects. The number and percentage of screen failure subjects will be summarized for each exclusion criteria met and/or inclusion criteria failed.

Disposition of all randomized subjects (ITT Analysis Set) will be summarized by treatment arms including:

- Number of subjects never vaccinated
- Safety Set
- Immunogenicity Analysis Set
- Per Protocol Set
- Number of subjects who completed study
- Number of subjects who prematurely discontinued study
- Primary reason for premature discontinuation of study

Primary reasons for study discontinuation collected on the Study Termination eCRF will be summarized with the following categories:

- Adverse Event
- Death
- Clinically Significant Hematological or Biochemical Changes
- Failure to Meet Continuation Criteria
- Symptoms or an Intercurrent Illness not Consistent with Protocol
- Lost to Follow-Up
- Physician Decision
- Pregnancy
- Study Terminated by Sponsor
- Withdrawal by Subject
- Other

Screen failure data will be listed by subject as collected based on screen failure subjects. Disposition data will be listed by subjects as collected based on ITT Analysis Set

5.2. Protocol Deviations

Protocol deviations will be documented by the clinical monitor throughout the course of monitoring visits. Significant protocol deviations will be summarized using the ITT Analysis Set during the study for the first primary database lock on Day 113 and final database lock on end of study.

A by subject listing will be provided based on the ITT Analysis Set including both the significant and non-significant protocol deviations. A separate listing will be provided on protocol deviations based on Immunogenicity Analysis Set but excluded from the PP Immunogenicity Analysis Set.

6. Demographics and Baseline Characteristics

6.1. Demographics

Demographic and baseline characteristics data to be analyzed will include age, sex, race, ethnicity, weight, height, and body mass index on the ITT Analysis set. Age will be calculated as (Date of randomization - Date of birth)/365.25.

The following characteristics will be summarized and presented as continuous variables:

- Age (years)
- Weight (kg)
- Height (cm)
- Body Mass Index (BMI) (kg/m²)

The following characteristics will be summarized and presented as categorical variables:

- Sex (Male, Female)
- Race (White, Black or African American, Asian, American Indian or Alaska Native, Native Hawaiian or Other Pacific Islander, Multiple, Other)
- Ethnicity (Hispanic or Latino, Not Hispanic or Latino)

6.2. Baseline Disease Characteristics and Substance Usage

History of tobacco usage (yes/no), Past pertussis vaccination (yes/no), and any past surgeries/significant procedures for medical conditions (yes/no) will be summarized and presented as categorical variables on the ITT Analysis Set.

A by-subject listing will be provided on the ITT Analysis set.

6.3. Medical History

Medical history will be summarized based on the ITT Analysis Set. Medical history will be coded according to Medical Drug Regulatory Activities (MedDRA) version 22.0 or above and will be summarized by system organ class (SOC) and preferred term (PT), with SOCs sorted alphabetically and PTs within each SOC in descending order of frequency. A by-subject listing on medical history will be provided based on the ITT analysis set.

7. Treatments and Medications

7.1. Prior and Concomitant Medications

Partial missing dates will be imputed as described in Appendix 13.4 for medications analysis. The Anatomical Therapeutic Chemical (ATC) coding scheme of the latest World Health Organization Drug Dictionary (WHODD) will be used to group medications into relevant categories.

7.1.1. Prior Medications

Prior medications are defined as non-study medications with a start date before the date of prime dose. Prior medications that continue on and after the date of prime dose will be reported as both prior and concomitant medications. Prior medications will be summarized based on the ITT Analysis Set by ATC2 level and preferred medication names, with ATC2 level sorted alphabetically and preferred names within each ATC2 level in descending order of frequency.

A by-subject listing will be provided for prior medications based on the ITT Analysis Set.

7.1.2. Concomitant Medications

Concomitant medications are defined as non-study medications (including herbal supplements, multivitamins, and over-the-counter medications) taken by the subject from the time of prime vaccination through 28 days after the boosting vaccination (or through early termination visit if prior to that time).

Concomitant medications will be summarized by ATC2 level and standardized medication names, with ATC2 level sorted alphabetically and standardized names within each ATC2 level in descending order of frequency. Summaries will be provided based on the Safety Analysis Set.

A by-subject listing will be provided for concomitant medications based on the Safety Analysis set.

7.2. Study Treatments

7.2.1. Treatment Compliance

The study vaccination will be administered to maintain the blind to site personnel conducting subject assessments. The location (in case of IM administration, right or left arm), date, and timing of all product administrations will be recorded in the subjects' eCRF. Compliance will be determined by the number and percentage of subjects who receive study vaccination.

Compliance rate will be summarized by counts and percentages for subjects receiving the prime vaccination, boost vaccination, and for those receiving both vaccinations (including a separate group of subjects who received different investigational products (IPs) at the prime and boost vaccination, if any) based on the ITT Analysis Set and Safety Analysis Set. For compliance rate of prime vaccination, subjects will be grouped into BPZE1 prime (A, B, A+B) and Boostrix prime (C, D, C+D) arms. For boost vaccination, subjects will be grouped into BPZE1 boost (A, C, A+C) and Placebo boost (B, D, B+D). For both vaccinations, subjects will be grouped into BPZE1 prime with BPZE1 boost (A), BPZE1 prime with no boost (B), Total Post BPZE1 prime (A+B), Boostrix prime with BPZE1 boost (C) and Boostrix prime with no boost (D), Total Post Boostrix prime (C+D), Total Post Booster BPZE1 (A+C).

Any deviations from the dosing schedule outside the defined visit windows (Appendix 13.1) will be flagged in the clinical database.

A by-subject listing will also be provided based on the Safety Analysis Set.

8. Immunogenicity Analyses

8.1. Primary Immunogenicity Analyses

The primary immunogenicity endpoint of this study is mucosal seroconversion (nasal mucosal secretion sampling) defined as the proportion of subjects who achieve seroconversion against at least 1 pertussis antigen (PT, FHA, PRN, FIM 2/3, or BPZE1 whole cell extract) in nasal secretions on Day 29 for the prime vaccination or Day 113 for the prime + boost vaccination.

Mucosal seroconversion is defined as a 2-fold increase over the baseline value (collected during screening) or a 4-fold increase over the minimal limit of assay detection (whenever the baseline value falls below the limits of assay detection) for any of the pertussis-specific antibodies (S-IgA ELISA): PT, FHA, PRN, FIM 2/3, or BPZE1 whole cell extract.

Seroconversion will be calculated based on absolute titer response (based on IgA) over baseline **and** by standardizing pertussis specific ELISA responses relative to non-pertussis specific total mucosal secretion (Total IgA). Overall mucosal seroconversion defined as either seroconversion based on absolute titer response (based on IgA) or seroconversion based on standardizing pertussis specific ELISA responses relative to non-pertussis specific total mucosal secretion (Total IgA).

Any pertussis antigen specific antibody titer (PT, FHA, PRN, FIM 2/3, or BPZE1 whole cell extract) from nasal mucosal sample that is below the minimal limit of assay detection will be imputed with a value equal to half of the minimal limit of assay detection of the antigen specific antibody titer.

The proportion of subjects who achieved mucosal seroconversion on Day 29/Visit 3 or Day 113/Visit 8 will be summarized based on the Immunogenicity Analysis Set. Baseline is defined as the last non-missing value collected before the prime vaccination.

Data will be summarized using frequency counts and percentages.

A by-subject listing will be provided for mucosal immunogenicity data as collected based on Immunogenicity Analysis Set.

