8.2.2. Secondary Mucosal Immunogenicity Analyses

Secondary mucosal immunogenicity endpoints are as described in Section 3.2.2.2.

Summaries and analyses will be the same as secondary systemic immunogenicity endpoints with the following exceptions:

1. the pre-boost baseline is defined as the value collected on Day 78/Visit 4 prior to boost vaccination. If the visit is missed on Day 78 but the subject arrives for boost vaccination, then a sample obtained prior to the vaccination will be used as the pre-boost value.
2. All mucosal immunogenicity endpoints will be calculated and summarized based on absolute titer response over baseline and by standardizing pertussis specific ELISA responses relative to non-pertussis specific total mucosal secretion of total IgA .

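### On the total-IgA-standardised scale, half-LOD values with no detectability condition let a fall in total IgA alone score some undetectable post-dose samples as responses

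*SAP*

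**What the plan says.** SAP 8.1 gives one definition of mucosal seroconversion: "a 2-fold increase over the baseline value (collected during screening" or, for a low baseline, "a 4-fold increase over the minimal limit of assay detection (whenever the baseline value falls below the limits of assay detection". It then calculates the endpoint on the absolute titre and also "by standardizing pertussis specific ELISA responses relative to non-pertussis specific total mucosal secretion (Total IgA". Either scale is enough: "Overall mucosal seroconversion defined as either seroconversion based on absolute titer response (based on IgA) or seroconversion based on standardizing".

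A nasal titre below the limit is "imputed with a value equal to half of the minimal limit of assay detection of the antigen specific antibody titer"; SAP 4.6 repeats the rule. SAP 8.2.1 says the limits will be set for the antibody titres, after assay validation and before database lock.

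Protocol 2.4.1 left the standardisation to be worked out during assay development and in the SAP. The SAP adds that the reference quantity is total IgA and that either scale suffices. It gives no ratio formula, no detection limit on the ratio scale, no rule for the ratio when the titre is below the limit, and no condition that the post-dose titre be detectable.

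SAP 8.2.2 carries both scales to the secondary endpoints: "All mucosal immunogenicity endpoints will be calculated and summarized based on absolute titer response over baseline and by standardizing". One of these is mucosal boosting (SAP 3.2.2.2, and 8.2.1.5 by way of 8.2.2): at least a 2-fold rise from the pre-boost sample to Day 113, with no detection-limit clause.

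**The concern.** The detection limit and the half-limit substitution are in titre units. Once a substituted value is divided by the sample's total IgA, an undetectable result becomes a number that rises whenever total IgA falls. A nasal sample with little total IgA can then look like an antibody response although no specific antibody was found in it.

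The standardised scale is one of the two primary calculations. Because either scale counts, the absolute-titre result does not protect the overall seroconversion proportion. All five antigens in a sample share one total-IgA value, so one low value moves every antigen together, and endpoints that require two or more antigens give little protection. No hypothesis is tested (SAP 4), so what is at stake is bias in the reported proportions, not type I error.

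**Working it through.** **The plan's own figure.** The documents give no figure for this rule. The only computed figure tied to the primary endpoint is the confidence-interval table (SAP Table 4-1, Protocol Table 7-1). Exact Clopper-Pearson limits reproduce all 20 cells to within 0.05 percentage points, for example 42.9 to 57.1 at N = 200 and 50%. The table has no bearing on the scoring rule.

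**Inputs.** From the SAP: the 2-fold rule, the 4 x LOD clause, half-LOD substitution and the 2-fold boost rule. Assumed, because the SAP gives no formula: standardised value = titre / total IgA. Let T0 and T1 be total IgA in the reference (baseline or pre-boost) and post-dose samples.

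**Case (i): seroconversion, baseline detectable, post-dose below LOD.** Let the baseline titre be b x LOD with b at least 1. It is not below the limit, so the plain 2-fold rule applies. The post-dose titre is set to 0.5 x LOD.

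- Standardised fold rise = (0.5 x LOD / T1) / (b x LOD / T0) = (0.5 / b) x (T0 / T1).
- It reaches 2 when T0 / T1 is at least 4b.
- b = 1 needs a 4-fold fall in total IgA, b = 2 an 8-fold fall, b = 4 a 16-fold fall.

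The 4 x LOD clause does not apply here, so no reading of it blocks the score.

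**Case (ii): mucosal boost, both titres below LOD.**

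- Standardised fold rise = (0.5 x LOD / T1) / (0.5 x LOD / T0) = T0 / T1.
- It reaches 2 when total IgA halves, for every undetectable antigen at once.

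**Seroconversion with both titres below LOD.** The 4 x LOD clause applies, and the result turns on how it is carried to the ratio:

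| Reading of the clause | Condition to score | Fall in total IgA needed |
|---|---|---|
| Kept on the raw titre | 0.5 x LOD >= 4 x LOD | never scores |
| Limit is 4 x LOD / T1 | 0.5 / T1 >= 4 / T1 | never scores |
| Limit is 4 x LOD / T0 | 0.5 / T1 >= 4 / T0 | 8-fold |
| Clause ignored, 2-fold rule on the ratio | T0 / T1 >= 2 | 2-fold |

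Protocol 7.7.1 and 7.7.3 state the rule without the below-limit condition. The endpoint definitions (Protocol 2.4.1 and 7.1, SAP 3.2.1.1 and 8.1) include it.

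**How likely a fall is.** The documents give no variability for total IgA. Assume independent samples, no true change, and a per-sample log10 SD of s. The log10 change is then Normal with mean 0 and SD s x sqrt(2), and P(fall of at least k-fold) = 1 - Phi(log10 k / (s x sqrt(2))).

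| s (log10) | 2-fold | 4-fold | 8-fold |
|---|---|---|---|
| 0.087 (natural-log SD 0.2) | 0.7% | about 0% | about 0% |
| 0.2 | 14.4% | 1.7% | 0.07% |
| 0.3 | 23.9% | 7.8% | 1.7% |
| 0.4 | 29.7% | 14.4% | 5.5% |

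For s = 0.3 and k = 2: 0.301 / 0.424 = 0.71, and the upper tail is 23.9%. The 2-fold column bears on case (ii). The 4-fold column bears on case (i) with baseline exactly at LOD. Each figure is conditional on the titre pattern of its case.

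**The case against.** The strongest reply is that the clause for below-limit baselines already covers the obvious case. Read naturally, it takes a subject with an undetectable baseline off the 2-fold rule, and the limit belongs to the antigen-specific titre. A subject undetectable at both visits whose total IgA halves is then not a seroconverter. That stands. A reader might infer that halving total IgA creates seroconversion in subjects who never had detectable antibody, or that 14% to 30% is a false-positive rate for the primary endpoint. The documents support neither: the first requires ignoring the clause, and the second takes a conditional probability, built on an assumed variance, for an endpoint rate.

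It can also be said that case (i) is a corner case. This is partly right. It needs a baseline at or just above the limit, and the fall required grows with baseline. The share of subjects in that position is unknown.

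Third, absolute-titre results are also reported for all mucosal endpoints and by-subject listings are planned, so a careful reader could find the artefact. That limits the harm but does not correct the overall seroconversion proportion, which either scale can satisfy.

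None of this answers case (ii): the boost definition has no detection-limit clause.

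**Conclusion.** The point holds in limited form. Taking the standardised value as titre over total IgA, the rules as written can score a standardised response in an undetectable post-dose sample in two cases: seroconversion from a baseline at or just above LOD (a 4-fold fall in total IgA at LOD, 8-fold at 2 x LOD), and mucosal boost with both titres below LOD (a 2-fold fall). The first can enter the overall primary proportion; the second affects the standardised boost endpoint.

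For seroconversion with both titres below LOD, the SAP does not fix the answer. Two readings never score it, one needs an 8-fold fall, and a 2-fold fall suffices only if the clause is ignored.

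The size cannot be derived from the documents. The chance of a 2-fold fall runs from about 0.7% to 30% over an assumed log10 SD of about 0.09 to 0.4, conditional on undetectable titres. The share of subjects with such titres is not given, so no effect on a reported proportion can be calculated. The change is worth making before database lock, but it does not threaten the trial's design.

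**What to change.** In SAP 8.1 and 8.2.2:

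- State the formula for the standardised value.
- State that being below the limit of detection is judged on the raw antigen-specific titre for both scales.
- Require a raw post-dose titre at or above LOD before an antigen can count as standardised seroconversion or standardised boost. This removes both cases at any fall in total IgA.
- For raw baselines below LOD, state the form of the 4 x LOD criterion: on the raw titre, or as 4 x LOD divided by post-dose total IgA. The two are equivalent, because both sides are divided by the same T1.

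No special GMFR rule is needed, such as setting the ratio to 1 when both titres are undetectable. That would treat doubly undetectable pairs differently from singly undetectable ones. With no true change in total IgA, log(T0 / T1) averages zero, so those pairs add noise but no systematic shift.

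The fix does not stop total IgA from moving results just above the limit. For example, baseline 1.1 x LOD, post-dose 1.0 x LOD and a 2.2-fold fall still give (1.0 / 1.1) x 2.2 = 2.0. Some sensitivity of this kind is inherent in standardising.

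The cost is a few sentences and one programming condition, with no new data or visits. The limits are themselves still to be set before database lock, so the rule can be fixed with them. The downside is that the standardised responder rate may fall slightly, including for some dilute samples.
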